Study Protocol and Statistical Analysis Plan

NIH #: 1R21CA224609-01A1

Official Title: Positive Psychology for Physical Activity Promotion

NCT #: NCT03826173

Date of document: Approved by the Brown University IRB on March 12, 2018

Engaging in regular physical activity (PA) is consistently inversely associated with risk of breast and colon cancers,³⁻¹⁷ with additional evidence for suggesting PA helps prevent endometrial,^{18,19} pancreatic,²⁰ and lung^{21,22} cancers. Despite these benefits, less than 5% of overweight and obese adults meet national guidelines for PA.⁴⁴ Moreover, overweight adults spend less time in PA than normal weight adults,⁴⁴⁻⁴⁸ and are more likely to discontinue PA programs.^{49,50} Affect (feeling good/bad) is important for promoting regular PA, as those who respond with less positive affect **during moderate intensity PA** are less likely to adopt a program of regular PA.²³⁻²⁸ Additionally, those experiencing lower positive affect and higher negative affect **outside the context of PA** are less likely to engage in PA.²⁹⁻³⁴ Given the importance of positive affect for adoption and maintenance of regular PA, intervention components that focus on enhancing positive affect may be a valuable addition to standard PA promotion interventions. Specifically, interventions derived from positive psychology⁵⁵ have shown promise in reducing depressive symptoms and increasing positive affect and are beginning to be applied to other areas of behavioral health.⁵⁶⁻⁵⁷ Consistent with the ORBIT model⁵² for developing behavioral interventions, the **aims of this project** are to, **first**, translate positive psychology theory into a 6-week, group-based positive psychology for PA promotion (PPPA) intervention for low-active overweight or obese adults (≥ 18 years; BMI 25-40), delivered at **local YMCAs**, and supplemented with **text messaging**. We will deliver the intervention prototype among a cohort of 10 participants. Participants and investigators will provide ongoing feedback regarding their experiences with the intervention in an iterative development process to refine the protocol. Our **second aim** is to test proof-of-concept and feasibility of PPPA in the context of a randomized pilot study among 60 low-active overweight or obese adults at local YMCAs. In an **additive design**, participants will be randomized in a 2:1 ratio to **PPPA** versus a **control** intervention including only the standard PA promotion components of the PPPA intervention (i.e., PA education, self-monitoring, and goal-setting), with **equal frequency of staff contact and text message delivery**. All participants will be followed for 6 months, and will receive a 6-month YMCA membership to equate access to PA facilities. We **hypothesize** that participants in PPPA, relative to the standard PA intervention will: demonstrate **equal or greater session treatment retention and satisfaction (H1)**; and **more min per week of PA** as measured by accelerometry at immediate post-treatment (week 7) and weeks 13 and week 26 (H2). As a secondary aim we will examine effect sizes for PPPA versus the standard PA intervention on putative mediators that may underlie the efficacy of PPPA in improving PA outcomes, including positive and negative affect, optimism, happiness, life satisfaction, social support for PA, and PA enjoyment. The proposed research will set the stage for an RCT to test a novel PA promotion intervention that can be readily disseminated.

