Aim 1: Intervention development and refinement (ORBIT Phase 1): The first aim of the project is to translate positive psychology theory and research into a 6-week, group-based positive psychology for PA promotion (PPPA) intervention for low-active overweight or obese adults, delivered at local YMCAs, and supplemented with text messaging. The in-person session and text-messaging protocol will be based on the team's previous and ongoing work developing and implementing positive psychology and smoking cessation interventions ([name], [name]), as well as our expertise in exercise promotion interventions ([name]; [name]). We will deliver the intervention prototype among a cohort of 10 low-active (< 60 min/week of structured PA) overweight or obese adults (≥ 18 years; BMI 25-40). Participants and clinician-investigators will provide ongoing feedback regarding their experiences with application of the intervention in an iterative development process to refine the protocol, improve the utility of the intervention and modify intervention materials. The milestone for Phase 1 is a finalized PPPA intervention protocol by month 6 of year 1.

Aim 2: Preliminary testing (ORBIT Phase 2): The second aim of the project is to test proof-of-concept and feasibility of PPPA. This will be accomplished in the context of a randomized pilot study among 60 low-active overweight or obese adults at local YMCAs. In an additive design, participants will be randomized in a 2:1 ratio to PPPA versus a control intervention including only the standard PA promotion components of the PPPA intervention (i.e., PA education, self-monitoring, and goal-setting), with equal frequency of staff contact and text message delivery. All participants will be followed for 6 months, including the 6-week treatment period, and will receive a 6-month YMCA membership to equate access to PA facilities. We hypothesize that participants in PPPA, relative to the standard PA intervention will: demonstrate equal or greater session treatment retention and satisfaction (H1); and more min per week of PA as measured by accelerometry at immediate post-treatment (week 7) and weeks 13 and week 26 (H2).

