C.2.e. Interventionist characteristics and training. The characteristics of the interventionist have implications for ultimate dissemination of the Positive Psychology for PA (PPPA) program should it show initial efficacy. A bachelor's-level RI will conduct the treatment, with oversight from the investigative team. The RI will be similar in training and experience to the community-level staff that we expect would ultimately deliver the treatment in a future effectiveness trial and upon dissemination of the program. Treatment manuals will be developed to ensure consistent delivery of the PPPA and Standard PA promotion (SPA) interventions. The RI will practice the treatment protocol with other staff and students until it is delivered consistently.

C.2.f. Treatment fidelity. A treatment fidelity checklist will be created for each session and completed at the end of each session by the RI. Additionally, all treatment sessions will be audio-recorded. Review of recordings along with a second completion of the checklist will be split among [name], [name], and [name], who will meet weekly with the RI to discuss any deviations from the treatment protocol. Although we do not expect deviations from the protocol, any such deviations will be addressed by the PI, with the RI retrained as needed. Weekly meetings will also be used to assess strengths and weaknesses of treatment components and suggest revisions to the protocol that will be implemented in the next phase of research (see below).

C.2.g. Assessment timeline. Assessments will be conducted at baseline, ongoing during the 6-week PPPA program, at week 7 (one week after the final PPPA intervention session) and at week 13 (3-month follow-up).

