Intervention feasibility and acceptability: We will record PPPA session attendance and responses to the evening text-messages as objective indices of feasibility and acceptability. Retention will be coded as a dichotomous variable with participants who complete the sixth and final treatment session characterized as treatment "completers" and those not attending the final session as "non-completers." Participants will complete a Treatment Strategies Questionnaire at sessions 2-6, which will assess frequency of use of specific PPPA strategies in the past week such as planning opportunities for PA and completing the 3 Good Things exercise.¹⁰⁸ Responses to the questions will be used to inform the treatment feedback process. Satisfaction will also be assessed with the Client Satisfaction Questionnaire, an 8-item questionnaire that will be administered at the 7-week follow-up to assess participant satisfaction with provided services (CSQ-8).¹⁰⁹ **Positive psychology measures and putative mediators:** The Values in Action Survey⁹⁷ will be administered to all participants at baseline, and participants will receive feedback on their 5 "Signature Strengths" derived from this measure.^{81,82} The following putative mediators will be assessed at mid-treatment (session 3), post-treatment (week 7), and 13-week follow-ups. Short-term changes in positive and negative affect will be assessed with the Positive and Negative Affect Scale.¹¹⁰ Trait optimism will be assessed with the well-validated revised Life Orientation Scale.¹¹¹ Subjective happiness and subjective well-being will be assessed with the 4-item Subjective Happiness Scale¹¹² and the 5-item Satisfaction with Life Scale.¹¹³ Social support will be assessed at baseline and follow-ups using the 13-item Social Support for Exercise Scale.¹¹⁴ Finally, PA enjoyment will be assessed with the 18-item Physical Activity Enjoyment Scale.¹¹⁵

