C.2.i. Intervention refinement. During the initial PPPA intervention group, the intervention manual and materials will be refined based on an iterative treatment development process. After each of the sessions is completed, participants will complete brief questionnaires on perceived session utility and their use of PPPA strategies in the past week. Open-ended questions will also assess the utility and acceptability of the treatment sessions and exercises. Intervention refinement will also be based on investigators' weekly reviews and discussion of the audio-recorded sessions. This will lead to a revised PPPA manual going into Phase 2.

C.3. Additional procedures for Aim 2: Preliminary testing (ORBIT phase 2).

Procedures for Aim 2 will be the same as Aim 1, with the following exceptions:

C.3.a. Recruitment, enrollment, and randomization. We will recruit 60 participants who will be randomized at a 2:1 ratio to PPPA treatment versus **standard PA promotion (SPA)** in order to focus resources on the PPPA program while still including a comparison for preliminary testing. We will run 4 groups of PPPA and 2 groups of SPA, with 10 participants per group. Urn randomization will be used to balance on sex and BMI.

C.3.b. PPPA condition. The PPPA condition will follow the revised treatment manual and text messaging program, based on feedback from Aim 1, but will follow the basic themes and procedures noted above.

C.3.c. SPA condition. The SPA condition will consist of the **core PA promotion content** (see above). To equate for session duration, additional information on health and wellness will be delivered by the staff, including topics such as skin care, alcohol use, and heart health. **Text messages** for the SPA condition will consist of reminders to engage in PA and other general motivational messages, thus controlling for total number of text messages. Because all of the PA-related content in the SPA condition will also be provided in the PPPA condition, this is essentially *an additive design, with an equal contact control*.

C.3.d. Additional 6-month follow-up and 6-month YMCA membership. For both conditions, YMCA memberships will be extended for 6 months, and an additional assessment will take place at month 6 (wk 26).

C.4. Participant retention, compliance, and incentives

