We expect from our prior research experience to be able to contact 85-95% of participants at each follow-up assessment.^{108,116,117} We will employ our previously successful procedures to maintain high follow-up rates.^{108,116-118} Additionally, participants will be paid \$25 for 7-week follow up, \$25 for the 13-week follow up, and (in Study 2) \$25 for the 26-week follow up. These payments are not contingent upon PA level. **C.5. Data analysis:** We will examine within-group changes from baseline in MVPA at 7 and 13 weeks. We will also tabulate scores on all treatment feasibility and acceptability measures, as well as baseline measures and putative mediators, to determine mean responses to these measures.

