Aim 2. We will focus on determining **effect sizes** for PPPA rather than strict statistical significance testing. At the same time, we are well aware of the dangers of relying exclusively on small-scale pilots to determine the promise of novel treatment approaches,¹¹⁹ as estimates from small samples tend to have large standard errors. Thus our hope is that we find a pattern of results that is supportive of the experimental treatment. Similar PPIs have shown medium to large effect sizes on depressive symptoms, positive affect, and happiness. Effect size estimates will include Cohen's *d* (for unadjusted between-group comparisons) and f^2 (for longitudinal multivariate models of treatment effect). For the purpose of estimating the effects of treatment on both MVPA and the putative mediators, we will fit a series of mixed effects regression models in which, for example, min/week of objectively measured MVPA at post treatment, and at 13 and 26 weeks will be simultaneously regressed on treatment group, baseline MVPA and variables not balanced by randomization. Models will allow for estimating both effects of treatment on MVPA post treatment, as well as maintenance of MVPA from 7 weeks through 6m. A similar strategy will be used to estimate effect sizes with respect to treatment effects on the putative mediators. We believe a sample size of 60 (40 intervention versus 20 control) should allow adequate examination of PPPA intervention effect sizes while staying within the scope of a developmental project. We recognize that only medium to large effect sizes will be likely to attain statistical significance with an unbalanced sample of this size. **Feasibility and acceptability:** Between-group differences for continuous measures (number of sessions attended and client satisfaction scores at post-treatment) will be conducted using analysis of variance and chi-squared analyses for dichotomous variables (treatment retention). We anticipate that treatment attendance and completion will either be equal or will be higher in the PPPA condition.

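### H1 counts equal retention and satisfaction as success, but a non-significant ANOVA or chi-squared result cannot affirm equality, and no interval is planned

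*Combined protocol and SAP*

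**What the plan says.** The opening summary and the Aim 2 paragraph both state H1: PPPA participants will "demonstrate equal or greater session treatment retention and satisfaction (H1"). The feasibility paragraph of C.5 repeats the expectation that attendance and completion will be no lower under PPPA.

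The measures are defined in C.2.h. "Retention will be coded as a dichotomous variable with participants who complete the sixth and final treatment session" counted as completers. Satisfaction is the CSQ-8, "administered at the 7-week follow-up to assess participant satisfaction with provided services".

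The analyses that C.5 names specifically for these measures are tests of between-group difference: ANOVA for the number of sessions attended and for "client satisfaction scores at post-treatment) will be conducted using analysis of variance and chi-squared analyses for dichotomous variables (treatment retention").

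Three other statements in the Aim 2 part of C.5 bear on the point. Aim 2 is to focus on effect sizes and not on strict significance testing. Cohen's d is listed for unadjusted between-group comparisons. Only medium to large effects are expected to reach significance at 40 versus 20. The analysis text attaches no confidence interval to any H1 measure, or to any other outcome, and does not say what would count as equal.

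**The concern.** H1 has two ways to succeed: PPPA does better, or PPPA does the same. A test of difference can show the first. For the second, the only result it can return is a failure to reject, and in a small sample that happens often whether the arms are the same or PPPA loses more people.

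H1 is one of the two Aim 2 hypotheses, and the study is meant to prepare a larger RCT. Whether the added positive-psychology content costs completers is a main feasibility input for that trial. If the report gives only test results for retention, its reader cannot tell how large a shortfall is still compatible with the data.

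**Working it through.** **Inputs from the documents.** 40 PPPA and 20 SPA (C.5, C.3.a); completion is binary (C.2.h); the team expects "to be able to contact 85-95% of participants at each follow-up assessment" (C.4). That rate concerns follow-up assessments, not attendance at session 6.

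**Assumptions.** Two-sided 0.05; SPA completion 85%, with 75% to 90% as the range; participants independent except in step 6. The documents give no alpha, completion rate, SD or intraclass correlation.

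**1. The plan's own statement about significance.** No numerical figure is given for H1, so only the qualitative remark can be checked. With 40 versus 20, noncentral-t power is 44% at d = 0.5 and 82% at d = 0.8. The smallest observed d that reaches p < 0.05 is 0.55. The remark is roughly right for observed effects and somewhat generous for a true medium effect.

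**2. How often the chi-squared test is non-significant.** Sum Binomial(40, p_PPPA) × Binomial(20, p_SPA) over all tables with uncorrected p ≥ 0.05:

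| SPA completion | equal | PPPA 10 points worse | PPPA 20 points worse |
|---|---|---|---|
| 75% | 95% | 88% | 67% |
| 85% | 96% | 88% | 62% |
| 90% | 96% | 86% | 59% |

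Fisher's exact test and the Yates correction give higher percentages throughout. For example, at SPA 85% and a 20-point deficit they give 69% and 77%. The plan does not say which variant it means.

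**3. One possible result: 26/40 (65%) versus 17/20 (85%).** Chi-squared = 60 × (26×3 − 17×14)² / (40×20×43×17) = 60 × 25,600 / 584,800 = 2.63, so p = 0.11 (Fisher 0.14, Yates 0.19). Wilson 95% limits are 0.495 to 0.779 for PPPA and 0.640 to 0.948 for SPA. Newcombe limits for the difference of −0.20:
- lower: −0.20 − √[(0.650 − 0.495)² + (0.948 − 0.850)²] = −0.38
- upper: −0.20 + √[(0.779 − 0.650)² + (0.850 − 0.640)²] = +0.05

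The test reports no significant difference. The interval shows that a shortfall of up to 38 points is not excluded.

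**4. Identical observed rates: 34/40 versus 17/20.** PPPA Wilson limits are 0.709 to 0.929. Lower limit: 0 − √[(0.850 − 0.709)² + (0.948 − 0.850)²] = −0.17; upper limit +0.22. At 75% or 90% observed in both arms the lower limit is −21 or −15 points.

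**5. Continuous measures.** The 95% half-width in SD units is t(0.975, N−2) × √(1/n1 + 1/n2).
- Sessions attended, 40 and 20: 2.002 × 0.274 = 0.55.
- CSQ-8, if the contact rate applies at week 7: 38 and 19 (95%) give 2.004 × 0.281 = 0.56; 34 and 17 (85%) give 2.010 × 0.297 = 0.60.

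**6. Clustering.** C.3.a says "We will run 4 groups of PPPA and 2 groups of SPA, with 10 participants per group". With an assumed intraclass correlation of 0.01 to 0.05, the design effect 1 + 9 × ICC is 1.09 to 1.45. Dividing the sample sizes in step 4 by it moves the lower limit from −17 to between −18 and −21 points. The intervals above are therefore probably too narrow.

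**7. Does the interval discriminate better?** No. At SPA 85% the Newcombe interval includes zero in 96% of trials with equal arms and 88% with a true 10-point deficit, much as the test does. Its lower limit lies above −10 points in only 21% of truly equal trials.

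**The case against.** The strongest defence is that this is a pilot that puts effect sizes before significance, warns that small-sample estimates have large standard errors, and words the feasibility expectation as an anticipation, not a claim to be confirmed. Cohen's d can be read as covering sessions attended and CSQ-8, and the list of effect sizes is open. Most of this stands, and it is why the weight is low. What remains is that d is a point estimate, that it does not suit a yes/no retention variable, and that the paragraph written for H1 names only tests.

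It is also fair to say that the missing interval is not peculiar to H1, since the analysis text gives none for MVPA or the mediators either. It matters more here because H1 is the hypothesis that counts no difference as success.

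A reader might go further in three ways that are not supported:
- **That the tests say nothing about the equal half of H1.** A significant deficit would refute it, and the non-significance rate does fall, from 96% to 62%, as the true deficit grows from 0 to 20 points at SPA 85%.
- **That the investigators will treat non-significance as equality.** No passage says so.
- **That an interval would separate equal arms from a 10-point deficit.** It uses the same 60 people and does not (step 7).

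**Conclusion.** The point holds in a limited form. The tests named for H1 can support greater or refute H1, but the result they will usually return cannot affirm equal, and nothing in the plan reports the shortfall that remains possible.

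Size: with SPA completion assumed at 85%, non-significance occurs in about 96%, 88% and 62% of trials for true deficits of 0, 10 and 20 points. Even identical observed rates of 85% leave a lower limit of −17 points. These figures rest on an assumed completion rate, two-sided 0.05, the uncorrected test and independent participants; the pattern is the same for SPA rates from 75% to 90%.

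This is a cheap improvement of minor weight. A reader might infer that Aim 2 needs a non-inferiority design. It does not: with 85% completion in both arms, one-sided 0.025 and 80% power, margins of 20, 15 and 10 points would take 114, 201 and 453 participants, which is outside what a developmental study claims to do.

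**What to change.** In the feasibility paragraph of C.5:

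- Make the main H1 result the PPPA minus SPA difference with a 95% confidence interval: a risk difference with a Newcombe or score interval for completion, and mean differences for sessions attended and CSQ-8.
- Keep ANOVA and chi-squared as secondary description, and name the chi-squared variant.
- Add a statement such as: H1 is descriptive; a non-significant difference will not be taken as equality; the intervals treat participants as independent, ignore clustering in the six treatment groups, and so may be too narrow.

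No margin is required. If the investigators want one, it should be fixed before Aim 2 randomization, because attendance is recorded as sessions run and the reviewing investigators "meet weekly with the RI to discuss any deviations from the treatment protocol".

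Cost: SAP wording only, with no extra data or participants. The downside is wide intervals (a lower limit near −17 points for completion at 85% in both arms; about 0.55 to 0.60 SD either way for the continuous measures). H1 becomes an estimate and not a confirmed claim, which fits the plan's stated focus on effect sizes.

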Missing data. Although our follow-up rates in previous studies have exceeded 90%,^{108,116,117} some data will inevitably be missing. The proposed regression models use a likelihood-based approach to estimation and thus makes use of all available data (on the intent to treat sample) without directly imputing missing outcomes, to produce consistent estimates of the effects. However, we will compare the robustness of our findings using other statistical approaches for handling missing data, including propensity scores (in which we first model missingness as a function of observable data and then use the inverse predicted probability of drop-out as weights in the subsequent regression model). Provided the data is missing at random (MAR) or that the probability of missingness can be fully explained by observable data, this approach produces asymptotically unbiased estimates. To allow for the possibility that the MAR assumption may not hold, we will also use a second approach, pattern mixture models, in which the distribution of the outcome is assumed to follow a mixture of two distributions: one for those who complete follow up and another for those who do not.

C.6. Timeline: Given our experience with similar research, we expect to finalize the PPPA manual prototype within the first month of the study period and be ready for recruitment and enrollment in the initial study cohort (Aim 1) by month 2. This will give us two months upon completion of the 6-week program (and 7- and 13-week follow-ups) to refine and revise the treatment protocol prior to enrollment for Study 2 at the start of month 6.

Protection of Human Subjects

1. Risks to the Subjects

1.a. Human Subjects Involvement, Characteristics, and Design.

Procedures for Aim 1: Intervention development and refinement (ORBIT phase 1)

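### The first missing-data check weights by the inverse probability of drop-out instead of the inverse probability of being observed

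*Combined protocol and SAP*

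**What the plan says.** The Missing data paragraph of section C.5 sets out a main analysis and two checks on it. For the main analysis, "The proposed regression models use a likelihood-based approach to estimation", with no weights. The plan then says "we will compare the robustness of our findings using other statistical approaches for handling missing data, including propensity scores". That step is described as one "in which we first model missingness as a function of observable data", after which the analyst will "then use the inverse predicted probability of drop-out as weights in the subsequent regression model". Under MAR, or if observable data fully explain missingness, the plan says "this approach produces asymptotically unbiased estimates". The second check is a pattern mixture model.

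Two other places matter for the consequences. The Aim 2 text of C.5 says the outcomes at the three follow-ups are "simultaneously regressed on treatment group, baseline MVPA and variables not balanced by randomization". Section C.3.a says "Urn randomization will be used to balance on sex and BMI". No other section defines the weight or mentions the probability of being observed or retained.

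**The concern.** A weighted regression of this kind lets the people who were seen stand in for similar people who were not. Someone who resembles the drop-outs should count for more. The weight as written is largest for those with the smallest chance of dropping out, so it moves the analysed sample further from the missing participants than no weighting would. The unbiasedness statement belongs to the other weight.

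This check exists to show whether the main result is robust. With inverted weights it could depart from the mixed model for a reason created by the weights, and the team could take that for sensitivity to missing data. It could also lose much of the effective sample in a 60-person pilot whose purpose is to report effect sizes.

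**Working it through.** The plan gives no figure of its own to reproduce on this point, so the check applies the stated weight.

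**Inputs from the document.** Expected follow-up is 85–95% at each assessment (C.4), so 5–15% are missing, or 60 × 0.05 = 3 to 60 × 0.15 = 9 people. The sample is 60, allocated 40 to 20 (C.5, Aim 2). The weight is 1/P(drop-out) (C.5, Missing data).

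**Assumed inputs.** How drop-out varies between participants, the stratum effects, the covariate coefficient and the drop-out slopes are all illustrative.

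**1. Algebra.** Let R = 1 if the outcome Y is observed and p = P(drop-out | X). Under MAR:
- weight 1/(1 − p): E[R·Y/(1 − p)] = E[Y];
- weight 1/p: E[R·Y/p] = E[Y·(1 − p)/p].

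Even after dividing by the mean weight, the second expression differs from E[Y] unless (1 − p)/p is unrelated to Y, for example when p is constant.

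**2. Two equal strata, same drop-out in both arms.** The share of total weight held by the low-drop-out stratum is w₁(1 − p₁) / [w₁(1 − p₁) + w₂(1 − p₂)]. It should be 50%.
- 5%/15% drop-out, as written: (0.95/0.05) / (0.95/0.05 + 0.85/0.15) = 19/24.67 = 77%.
- 5%/25% drop-out, as written: 19/(19 + 3) = 86%.
- Unweighted: 0.95/1.80 = 53% and 0.95/1.70 = 56%.

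The estimate is the share-weighted mean of the stratum effects. The true mean is 40 min/week, and correct weights give 40.0 in every row.

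| Effects, low/high drop-out stratum | 5%/15% as written | 5%/15% unweighted | 5%/25% as written | 5%/25% unweighted |
|---|---|---|---|---|
| 40/40 | 40.0 | 40.0 | 40.0 | 40.0 |
| 45/35 | 42.7 | 40.3 | 43.6 | 40.6 |
| 50/30 | 45.4 | 40.6 | 47.3 | 41.2 |
| 60/20 | 50.8 | 41.1 | 54.5 | 42.4 |

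**3. Precision.** The Kish effective sample size is (Σw)²/Σw², with 30 people per stratum.
- 5%/25%: 28.5 + 22.5 = 51 completers, with written weights 20 and 4. This gives 660²/11,760 = 37.0, against 50.3 with correct weights.
- 5%/15%: 28.5 + 25.5 = 54 completers, with written weights 20 and 6.67. This gives 740²/12,533 = 43.7, against 53.8 with correct weights.

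**4. Drop-out driven by a prognostic covariate in the PPPA arm only.** Let x be standard normal with outcome coefficient 0.4, a true difference of 0.30 SD, and log-odds of drop-out a + bx. Then (1 − p)/p = exp(−a − bx), and reweighting x by this factor moves its mean to −b. With x outside the outcome model, the written weights give 0.30 − 0.4b:
- b = +1: −0.10 (unweighted 0.26);
- b = −1: 0.70 (unweighted 0.34);
- b = +0.5: 0.10 (unweighted 0.28).

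A simulation with N = 2,000,000, 2:1 allocation and 10% drop-out gave the same values, and 0.30 with correct weights. With x in the model, all three methods give 0.30.

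**5. Drop-out alike in both arms, slope 1.** With no effect modification the estimate is 0.30 with or without adjustment. The effective sample falls to 40% of completers, against 99% with correct weights. If the effect changes by 0.1 SD per SD of x, the written weights give 0.30 ∓ 0.1 × 1 = 0.20 or 0.40, even with the main effect of x in the model. Unweighted gives 0.29 or 0.31, and correct weights give 0.30.

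**6. Drop-out driven by early response in the PPPA arm only.** In a separate simulation the true effect was 0.50, about 8% were missing, and the regression was on treatment and baseline. The estimates were 0.544 unweighted, 0.503 with correct weights and 1.062 as written. With N = 60 and 20,000 replicates they were 0.540, 0.501 and 1.017.

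**The case against.** The strongest reply is that this is a slip of the pen. The paragraph names propensity scores, models missingness on observed data and states the MAR condition, which together describe standard inverse-probability weighting. An experienced analyst would probably run that. This is fair, and it means the inverted weight and the false unbiasedness claim are one fault, not two. But the phrase is the only definition in the plan. An analyst who follows it inverts the weights, and one who silently corrects it departs from the plan.

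Second, the magnitudes rest on assumptions. The largest departures need stratum effects of 60 against 20, or strong drop-out dependence in one arm only, and the document supports neither. The simulations use a single outcome and true drop-out probabilities, whereas the plan has a three-visit model with fitted ones; someone lost after week 7 still contributes there. This stands: the figures show direction and possibility, not an expected size.

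Third, covariate adjustment may protect the contrast. It does if every driver of drop-out is in a correctly specified outcome model and none modifies the effect. The plan's rule admits baseline MVPA and unbalanced variables. Sex and BMI are balanced by design and so might stay out, but urn randomization does not guarantee balance in 60 people, and nothing shows that they drive drop-out. Protection is possible but not assured.

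Finally, only one sensitivity analysis in a pilot is involved. That limits the severity and does not remove the error.

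**Conclusion.** The concern holds. As written, the weight is inverted, and the unbiasedness statement attached to it is false in general. The treatment contrast is biased in two situations: drop-out depends on something that modifies the effect, or it depends differently by arm on a prognostic variable outside the outcome model. If drop-out acts alike in both arms with a homogeneous effect, or all its drivers are in a correctly specified outcome model, mainly precision is lost.

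At 10% overall drop-out (5%/15%), within the plan's expected range, moderate effect modification moves 40 to 45.4 min/week and cuts 54 completers to an effective 43.7. Only the overall follow-up range comes from the document. The main likelihood-based model and the pattern mixture check do not use the weight, so the primary estimate is not threatened. The point should be fixed, with high confidence that the text is wrong as it stands.

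**What to change.** In the Missing data paragraph of C.5, replace the weight definition with wording such as: *each observed outcome is weighted by the inverse of its predicted probability of being observed at that follow-up, that is, 1/(1 − predicted drop-out probability)*. Because outcomes are taken at weeks 7, 13 and 26, each visit needs its own predicted probability. With about 3 to 9 people missing per visit, the missingness model can support only a few predictors. Stabilising the weights is optional.

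The rest of the paragraph can stay, with the proviso that the unbiasedness statement also needs a correctly specified missingness model. The change is one phrase in the analysis section and costs no data, participants or resources.
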